15.2. Patient withdrawal

Patients may withdraw from the study at any time at their own request, or they may be withdrawn at any time at the discretion of the investigator, in consultation with Executive committee of this study if needed, for safety, behavioral, or administrative reasons. In any circumstance, every effort should be made to document subject outcome, if applicable. The investigator should inquire about the reason for withdrawal and follow-up with the subject regarding any unresolved adverse events until the event resolve or stabilize at a level acceptable to the investigator.

If the patient withdraws from the study, and also withdraws consent for disclosure of future information, no further evaluations should be performed, and no additional data should be

collected. JBCRG and Pfizer may retain and continue to use any data collected before such withdrawal of consent.

15.3. Institutional Review Board (IRB)/Independent Ethics Committee (IEC)

It is the responsibility of the investigator to have prospective approval of the study protocol, protocol amendments, informed consent documents, and other relevant documents from the IRB/IEC. All correspondence with the IRB/IEC should be retained in the investigator file. Copies of IRB/IEC approvals should be forwarded to JBCRG office and Pfizer.

The investigator must obtain IRB/IEC review and approval for the continuation of the study at least once a year. For annual contract renewal, the standard procedure of each institution shall be followed.

The only circumstance in which an amendment may be initiated prior to IRB/IEC approval is where the change is necessary to eliminate apparent immediate hazards to the subjects. In that event, the investigator must notify the IRB/IEC and Pfizer in writing immediately after the implementation.

15.4. Ethical Conduct of the Study

The study will be conducted in accordance with the protocol, legal and regulatory requirements, and the general principles set forth in the International Ethical Guidelines for Biomedical Research Involving Human Subjects (Council for International Organizations of Medical Sciences 2002), ICH Guideline for Good Clinical Practice, Ethical Guidelines for Medical and Health Research Involving Human Subjects issued by the Ministry of Health, Labour and Welfare (MHLW), and the Declaration of Helsinki.

16. MANAGEMENT AND REPORTING OF ADVERSE EVENTS/ADVERSE REACTIONS REQUIREMENTS

This study includes qualifying diagnostic or monitoring procedures required per protocol to collect clinical data needed to meet the study objectives, which are not standard-of-care but that do not pose more than a minimal risk or burden to the study subject. The qualifying procedure in this study is physical activity data collection using wearable device.

16.1. Adverse Events (AE)

An AE is defined as any untoward medical occurrence and can therefore be any unfavorable and unintended sign (including an abnormal laboratory finding), symptom, or disease, whether or not related to the subject's participation in the study.

AE reporting period for each subject begins from the time the subject provides informed consent, through the end of the observation period of the study which must include at least 28 calendar days following the last administration of the drug under study. **Any AE related to**

PFIZER CONFIDENTIAL

above procedure that occurs from the time the subject consents to the clinical research through and including 12 hours after completion of the qualifying procedure must be recorded. The investigator is required to assess whether the AE may be related to the subject's participation in the study. All AEs (ie, serious and non-serious, including those attributed to qualifying procedure identified as research-related injury) are collected in the clinical study database.

The investigator must pursue and obtain information adequate to determine the outcome of the AE and to assess whether it meets the criteria for classification as a research-related injury requiring immediate notification to Pfizer as described below.

16.2. Research-Related Injury

Should a subject, in the investigator's opinion, suffer a medically important research-related injury caused by their participation in the study, the designated Pfizer clinician or medical monitor must be notified immediately.

A medically important research-related injury is any untoward medical occurrence that:

- Results in death;
- Is life-threatening (immediate risk of death);
- Requires inpatient hospitalization or prolongation of existing hospitalization;
- Results in persistent or significant disability/incapacity (substantial disruption of the ability to conduct normal life functions);
- Results in congenital anomaly/birth defect.

Medical and scientific judgment is exercised in determining whether an injury is an important medical event. An important medical event may not be immediately life-threatening and/or result in death or hospitalization. However, if it is determined that the event may jeopardize the subject or may require intervention to prevent one of the other outcomes listed in the definition above, the important medical event should be reported as a research-related injury.

An investigator may be requested by the designated Pfizer clinician or medical monitor to obtain specific additional follow-up information in an expedited fashion. In general, this will include a description of the injury in sufficient detail to allow for a complete medical assessment of the case and independent determination of possible causality. Information on other possible causes of the event, such as concomitant treatments, vaccines, and/or illnesses must be provided. In the case of a subject death, a summary of available autopsy findings must be submitted as soon as possible to Pfizer or its designated representative.

PFIZER CONFIDENTIAL

The table below summarizes the requirements for recording safety events on the CRF and for reporting safety events on the Clinical Trial (CT) Serious Adverse Event (SAE) Report Form to Pfizer Safety. These requirements are delineated for four types of events: (1) serious adverse events (SAEs); (2) non-serious AEs (as applicable); (3) scenarios involving drug exposure during pregnancy or breast feeding, and occupational exposure; and (4) scenarios involving medication errors. These events are defined in the section "Definitions of safety events". Of note, treatment for advanced breast cancer administered within the observation period of this study (ie, palbociclib plus endocrine therapy or endocrine monotherapy) is described as "drug under study".

Safety event	Recorded on the CRF	Reported on the CT SAE Report Form to Pfizer Safety within 24 hours of awareness
SAE	All	All
Non-serious AE	All	None
Scenarios involving exposure to a drug under study, including exposure during pregnancy, exposure during breast feeding, and occupational exposure	All (regardless of whether associated with an AE), except occupational exposure	All (regardless of whether associated with an AE) Note: Any serious associated adverse event is reported together with the exposure scenario. For occupational exposure, both serious and non-serious AEs are reported

Events listed in the table above that require reporting to Pfizer Safety on the CT SAE Report Form within 24 hours of awareness of the event by the investigator are to be reported regardless of whether the event is determined by the investigator to be related to the drug under study. In particular, if the SAE is fatal or life-threatening, notification to Pfizer Safety must be made immediately, irrespective of the extent of available event information. This time frame also applies to additional new (follow-up) information on previously forwarded reports. In the rare situation that the investigator does not become immediately aware of the occurrence of an event, the investigator must report the event within 24 hours after learning of it and document the time of his/her first awareness of the event.

For each event, the investigator must pursue and obtain adequate information both to determine the outcome and to assess whether it meets the criteria for classification as an SAE (see the Serious Adverse Events section below). In addition, the investigator may be requested by Pfizer Safety to obtain specific follow-up information in an expedited fashion. This information is more detailed than that recorded on the CRF. In general, this will include

a description of the event in sufficient detail to allow for a complete medical assessment of the case and independent determination of possible causality. Any information relevant to the event, such as concomitant medications and illnesses, must be provided. In the case of a subject death, a summary of available autopsy findings must be submitted as soon as possible to Pfizer Safety. Any pertinent additional information must be reported on the CT SAE Report Form; additional source documents (eg, medical records, CRF, laboratory data) are to be sent to Pfizer Safety **ONLY** upon request.

As part of ongoing safety reviews conducted by the sponsor, any non-serious AE that is determined by the sponsor to be serious will be reported by the sponsor as an SAE. To assist in the determination of case seriousness, further information may be requested from the investigator to provide clarity and understanding of the event in the context of the clinical study.

16.2.1. Additional Details On Recording Adverse Events on the CRF

All events detailed in the table above will be recorded on the AE page(s) of the CRF. It should be noted that the CT SAE Report Form for reporting of SAE information is not the same as the AE page of the CRF. When the same data are collected, the forms must be completed in a consistent manner. AEs should be recorded using concise medical terminology and the same AE term should be used on both the CRF and the CT SAE Report Form for reporting of SAE information.

16.2.2. Eliciting Adverse Event Information

The investigator is to record on the CRF all directly observed AEs and all AEs spontaneously reported by the study subject. In addition, each study subject will be questioned about the occurrence of AEs in a non-leading manner.

16.2.3. Withdrawal From the Study Due to Adverse Events (see also the Subject Withdrawal section)

Withdrawal due to AEs should be distinguished from withdrawal due to other causes, according to the definition of AE noted below, and recorded on the CRF.

When a subject withdraws from the study because of an SAE, the SAE must be recorded on the CRF and reported, as appropriate, on the CT SAE Report Form, in accordance with the Requirements section above.

16.2.4. Time Period for Collecting AE/SAE Information

The time period for actively eliciting and collecting AEs and SAEs (“active collection period”) for each subject begins from the time the subject provides informed consent, which is obtained before the subject’s participation in the study (ie, before undergoing any study-related procedure and/or receiving the marketed product under study), through the end of the

observation period of the study which must include at least 28 calendar days following the last administration of the drug under study.

For subjects who are screen failures, the active collection period ends when screen failure status is determined.

16.2.4.1. Reporting SAEs to Pfizer Safety

All SAEs occurring in a subject during the active collection period are reported to Pfizer Safety on the CT SAE Report Form.

SAEs occurring in a subject after the active collection period has ended are reported to Pfizer Safety if the investigator becomes aware of them; at a minimum, all SAEs that the investigator believes have at least a reasonable possibility of being related to drug under study must be reported to Pfizer Safety.

Follow up by the investigator continues throughout and after the active collection period and until the event or its sequelae resolve or stabilize at a level acceptable to the investigator, and Pfizer concurs with that assessment.

If a patient begins a new anticancer therapy, SAEs occurring during the above-indicated active collection period must still be reported to Pfizer Safety irrespective of any intervening treatment.

16.2.4.2. Recording Non-serious AEs and SAEs on the CRF

During the active collection period, both non-serious AEs and SAEs are recorded on the CRF.

Follow-up by the investigator may be required until the event or its sequelae resolve or stabilize at a level acceptable to the investigator, and Pfizer concurs with that assessment.

If a patient begins a new anticancer therapy, the recording period for non-serious AEs ends at the time the new treatment is started; however, SAEs and research-related injury due to wearable device must continue to be recorded on the CRF during the above-indicated active collection period.

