6. SCHEDULE OF ACTIVITIES

Refer to STUDY PROCEDURES and ASSESSMENTS sections of the protocol for detailed information on each procedure and assessment required for compliance with the protocol.

Procedure / Assessment	Screening	Baseline	Observation period (6 cycles; 24 weeks) ^j		End of Study ^c
			Weekly ^a	Cycle-base ^b	
Time Window			+ 3 days ^d	+ 7 days ^d	
Informed consent	X				
CRF data					
Patient baseline characteristics; Demography, Height, Weight, Medical history, Prior treatment and surgery history, Primary diagnosis, Site of metastatic and disease, Menopausal status, Treatment being initiated, Line of therapy		X			
ECOG performance status ^k		X	↔X↔		X
Adverse event monitoring (eg, type, grade) ^e			↔X↔		
Treatment (eg, type, duration) ^f			↔X↔		
Palbociclib dosing modification ^g			↔X↔		
Concomitant Medication (Surgery, Radiotherapy)			↔X↔		
Disease progression (if applicable)			↔X↔		
Initial treatment discontinuation (if applicable)			↔X↔		
Study withdrawal (if applicable)			↔X↔		
Study completion					X
PRO data via smartphone-based application					
Patient baseline characteristics; Education, Employment		X ⁱ			
EORTC-QLQ-C30		X ⁱ		X	
PRO-CTCAE ^h		X ⁱ	X		
Overall satisfaction with treatment				X	

PFIZER CONFIDENTIAL

Procedure / Assessment	Screening	Baseline	Observation period (6 cycles; 24 weeks) ^j		End of Study ^c
			Weekly ^a	Cycle-base ^b	
Time Window			+ 3 days ^d	+ 7 days ^d	
Physical activity data via wearable device					
Physical activity		X	↔X↔		

- a. Weekly assessment of PRO-CTCAE will be conducted based on Cycle 1 Day 1 regardless of cycle delay.
- b. Cycle-based assessment of EORTC-QLQ-C30 and Treatment satisfaction will be conducted on Day 15 of each cycle.
- c. End of study is defined as end of 6 cycles of initiated treatment. If patients discontinue the initiated treatment before completion of 6 cycles (eg, due to disease progression) and switch to another treatment, end of study will be end of 24 weeks after initiation of initial treatment. In this case, to assess association between change in QOL and physical activity versus disease progression, data collection [including PROs (EORTC-QLQ-C30 and PRO-CTCAE) and physical activity evaluation, EDC data entry] will continue to the end of the study (ie, 24 weeks after the start of the study) even if the treatment is switched to another treatment.

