8. RESEARCH QUESTION AND OBJECTIVES

8.1. Research Objectives

Primary objective

Assess change in (1) PRO as measured by EORTC-QLQ-C30 collected via smartphone-based application and (2) physical activity as measured by wearable device in Japanese patients with HR+/HER2- advanced breast cancer receiving below endocrine-based treatment as first or second line setting:

1. Palbociclib plus endocrine therapy (Group 1) or
2. Endocrine monotherapy (Group 2)

NOTE: The study is not intended to compare outcomes between the two groups as primary objective.

Secondary objectives

The following research objectives will be addressed separately for both Group 1 and 2.

- Assess the association between change in EORTC-QLQ-C30 and physical activity versus investigator-reported adverse event (AE)
- Assess the association between change in EORTC-QLQ-C30 and physical activity versus patient-reported symptom as measured by PRO-CTCAE collected via smartphone-based application
- Assess the association between change in EORTC-QLQ-C30 versus change in physical activity

- Assess the association between change in EORTC-QLQ-C30 and physical activity versus disease progression
- Assess the feasibility of collecting physical activity data with wearable device in Japanese patients with advanced breast cancer
- Assess patient's treatment satisfaction (collected as single item via smartphone-based application)
- Evaluate concordance and discordance between investigator-assessed AE versus PRO-CTCAE
- Characterize patients with HR+/HER2- ABC initiating each group treatment (eg, baseline patient demographics and clinical characteristics)

The following research objectives will be addressed Group 1 only.

- Describe dosing patterns (eg, dose reduction, dose interruptions, cycle delay)

CCI

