Patients will complete PRO assessment in weekly, and cycle-basis and wear the wearable device for 6 cycles. At the patients' regular clinical visits at approximately 30 day interval, they will bring the device worn in the past period, and study site staff will confirm if the returned wearable device is still functional and upload the physical activity data through Actigraph application (ie, ActiSync) into the Actigraph cloud system (ie, Actigraph CentrePoint). Detailed information will be included in User Manual and training for Actigraph CentrePoint for the sites. For the PRO and physical activity data collected from the patient, the data entry status or wearing status will be confirmed, but the data itself will not be confirmed. In addition, investigators or study site staff will complete eCRF to capture treatment changes and clinical outcomes (eg, adverse event) for 6 cycles after enrollment listed in SCHEDULE OF ACTIVITIES.

If a patient has not entered any data through ePRO application for 4 consecutive weeks or if a patient has not worn the wearable device for 4 consecutive weeks, the study site staff will be notified and asked to reach out to the patient.

Even if patients discontinue the initiated treatment before completion of 6 cycles and switch to another treatment, to assess association between change in QoL and physical activity versus disease progression, data collection (including PROs [EORTC-QLQ-C30 and PRO-CTCAE] and physical activity evaluation, EDC data entry) will continue to the end of the study (ie, 24 weeks after initiation of initial treatment).

End of Study

End of study is defined as end of 6 cycles of initiated treatment. If patients discontinue the initiated treatment before completion of 6 cycles (eg, due to disease progression) and switch to another treatment, end of study will be end of 24 weeks after initiation of initial treatment.

Investigators or study site staff will complete CRF to capture End of Study information listed in Section 6 SCHEDULE OF ACTIVITIES.

Patients will return the wearable device to study site staff. Study site staff will stop the collection of the physical activity data via configuration in Actigraph system (ie, Actigraph CentrePoint). Detailed information will be included in User Manual and training for Actigraph CentrePoint for the sites.

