6.2. Secondary Endpoint(s)

6.2.1. EORTC-QLQ-C30 scores

- ✓ The same analysis for other 14 scales of EORTC-QLQ-C30 (5 functional scales [physical, role, emotional, cognitive, and social functioning], 8 symptom scales [fatigue, nausea/vomiting, pain, dyspnea, sleep disturbance, appetite loss, constipation, and diarrhea], and financial difficulties scale) are performed as for global health status.
- ✓ Following analyses of 5 functional scales and Global health status scale of EORTC-QLQ-C30 are performed to assess the associations as follows:

When associations for group 1 and 2 were similar, the group 1 and 2 will be pooled.

- Tabulate patients with and without selected investigator-reported AE at each cycle, summarize the mean values of change in EORTC-QLQ-C30 from baseline at each cycle in each tabulated population, and compare the results at Cycle 1 and Cycle 3 using t-test
- Tabulate patients with and without symptom of PRO-CTCAE at each cycle, summarize the mean values of change in EORTC-QLQ-C30 from baseline at each cycle in each tabulated population, and compare the results at Cycle 1 and Cycle 3 using t-test
- Tabulate patients with disease progression during the observation period, and summarize the mean values of EORTC-QLQ-C30 before and after disease progression

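### Non-serious AE recording stops when a new anticancer therapy starts, PRO and activity data do not, and the SAP's investigator-AE tables and kappa have no matching cut

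*Protocol*

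**What the plan says.** **AE recording.** Protocol 16.2.4.2 deals directly with patients who begin a new anticancer therapy: "the recording period for non-serious AEs ends at the time the new treatment is started", whereas "SAEs and research-related injury due to wearable device must continue to be recorded on the CRF". Protocol 16.2.4 otherwise runs active AE collection from consent to the end of the observation period.

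**PRO and activity data.** For patients who stop the initial treatment early and switch, Protocol 6 (note c) says that "data collection [including PROs (EORTC-QLQ-C30 and PRO-CTCAE) and physical activity evaluation, EDC data entry] will continue to the end of the study". Protocol 10 repeats that collection "will continue to the end of the study (ie, 24 weeks after initiation of initial treatment").

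**General AE statements.** Protocol 16.1 says that "All AEs (ie, serious and non-serious, including those attributed to qualifying procedure identified as research-related injury) are collected in the clinical study database". In Protocol 16.2 a table, introduced by "The table below summarizes the requirements for recording safety events on the CRF", marks non-serious AEs as all recorded.

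**Analyses that use investigator AEs.** A secondary objective in Protocol 8.1 is to "Evaluate concordance and discordance between investigator-assessed AE versus PRO-CTCAE". SAP 6.2.1 will "Tabulate patients with and without selected investigator-reported AE at each cycle", summarise QLQ-C30 change in each subset, and apply t-tests at Cycles 1 and 3. SAP 6.2.2 does the same for activity metrics. SAP 6.2.5 plans a contingency table and a weighted kappa.

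**Nearby rules.** SAP 6.6 ends toxicity assessment at new treatment or 28 days after the last dose, whichever is earlier, and adds later toxicities if they were recorded. It stands under the safety summaries, and SAP 6.2 does not refer to it. SAP 5.3 covers missing data in the primary analysis and PRO scoring, not AE status.

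**The concern.** After a switch, one side of the comparison can stop by rule while the other continues by design. The gap concerns non-serious events, which is where one would expect most fatigue and pain, the two PRO-CTCAE symptoms, to fall.

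A table with only two categories has no place for a patient whose AE status was not collected. If such patients land in the without-AE category, that group takes in patients who had unrecorded events, and the contrast between the categories shrinks. In the kappa, a symptom that the patient reports against an AE that nobody was required to record looks like disagreement between patient and investigator. Protocol 11 chose fatigue and pain because they are often underestimated, so the artefact would run in the expected direction and could be taken as confirming it. Switching is also tied to progression, so the affected records are not a random subset.

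**Working it through.** The documents give no switch rate and no kappa, so there is no plan figure to reproduce. What follows is an illustration of size.

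**1. Share switched.** Inputs: Japanese subgroup median PFS of 22.2 and 13.8 months (first-line trial) and 13.6 and 11.2 months (later-line trial), from Protocol 7. Assumptions: exponential PFS, a switch at progression or after a fixed lag, and 30.4375 days per month.

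Share switched by time t = 1 − 0.5^((t − lag)/median). Elapsed time is 14 days at Cycle 1 Day 15, 70 days at Cycle 3 Day 15 and 168 days at week 24. Example: 70 days is 2.30 months, and 1 − 0.5^(2.30/11.2) = 0.133.

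| Median (months) | C1 D15 | C3 D15 | Week 24 | Post-switch share of 24-week patient-time |
|---|---|---|---|---|
| 22.2 | 0.014 | 0.069 | 0.158 | 0.081 |
| 13.8 | 0.023 | 0.109 | 0.242 | 0.127 |
| 13.6 | 0.023 | 0.111 | 0.245 | 0.128 |
| 11.2 | 0.028 | 0.133 | 0.289 | 0.153 |

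With an assumed 28-day lag from progression to switch, the ranges are 0, 0.042-0.082, 0.134-0.248 and 0.057-0.108.

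**2. With/without-AE contrast.** Let p be AE prevalence and s the share switched. If no post-switch AE is on record and uncollected counts as no AE, the contaminated share of the without-AE category is q = ps/(ps + 1 − p). A true 10-point contrast becomes 10(1 − q), if p and the mean changes are the same before and after the switch. With p assumed to be 0.4:

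- Cycle 3 Day 15, s = 0.069 to 0.133: q = 0.044 to 0.081, contrast 9.6 to 9.2.
- Cycle 6 Day 15 (154 days), s = 0.146 to 0.269: q = 0.089 to 0.152, contrast 9.1 to 8.5.

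**3. Kappa, binary, pooled over patient-time.** Assumed symptom prevalence 0.4, investigator sensitivity 0.7, specificity 0.9. Cells: both 0.28, AE only 0.06, PRO only 0.12, neither 0.54.

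- Observed agreement 0.82; expected 0.34 × 0.4 + 0.66 × 0.6 = 0.532; kappa = (0.82 − 0.532)/(1 − 0.532) = 0.615.
- If a share f of patient-time carries no AE record, both AE-positive cells are multiplied by 1 − f. At f = 0.153: observed 0.786, expected 0.542, kappa 0.533. At f = 0.081: kappa 0.572.
- Drop: 0.04-0.08. If half of post-switch AEs are on record, 0.02-0.04. With the lag, 0.03-0.06 and 0.02-0.03.

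**4. Kappa per patient (ever/never).** Assumed onset shares over Cycles 1 to 6 are 0.50/0.20/0.10/0.10/0.05/0.05, and an AE is lost if its onset follows the switch. Lost share is 0.045-0.086 without lag and 0.025-0.047 with it. Kappa is 0.591-0.569 and 0.602-0.590, a drop of 0.01-0.05.

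**5. Sensitivity.**

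- Prevalence 0.2-0.6 with sensitivity/specificity 0.5/0.9, 0.7/0.9 or 0.7/0.8 (no lag, none on record): pooled drop 0.02-0.10, per-patient drop 0.01-0.06.
- An assumed four-grade table behaves alike: linear-weighted kappa goes from 0.586 to 0.549-0.515, and quadratic from 0.676 to 0.631-0.590.
- The shortest overall-trial median in Protocol 7, 3.8 months (placebo plus fulvestrant), is an extreme: 0.343 switched by Cycle 3 Day 15, 0.37 of patient-time post-switch, and kappa 0.41 by the formula in step 3.
- Not modelled: switches for other reasons, loss of ePRO responses after a switch, and cycle numbering after a switch.

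**The case against.** **The protocol contradicts itself on AE recording.** A reader might infer this from Protocol 6, 10, 16.1 and 16.2. The documents do not support it. Section 16.2.4.2 is the only rule written for the time after a new therapy. Section 16.1 and the 16.2 table say which classes of event are recorded. Continued EDC entry fits with 16.2.4.2, because treatment, progression and SAE data are still entered. A clarifying sentence is enough.

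**The SAP will count uncollected AEs as no AE.** It does not say so. That is the literal result of a two-category split, not a stated rule. Part of SAP 5.2 is blacked out directly after its sentence on AE-association tests, so only the visible text can be called silent.

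**SAP 6.6 already supplies the window.** This stands in part: 6.6 and 16.2.4.2 agree on stopping at new treatment. But 6.6 stands under safety summaries and nothing carries it into 6.2. Its other limit, 28 days after the last dose, does not undermine a cut at new therapy. Protocol 16.2.4 continues collection to the end of observation when no new therapy starts, and 6.6 itself admits later recorded toxicities.

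**The effect is small where anything is tested.** This stands. Only Cycles 1 and 3 have t-tests, with 0-3% and 4-13% switched. With 80 patients, 40% with an AE and an assumed SD of 15-25, the standard error of the contrast is SD × √(1/32 + 1/48), or 3.4-5.7 points, against a loss of 0.4-0.8 points at Cycle 3. The study is descriptive and bases no decision on a test.

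**Conclusion.** The concern holds as a mismatch between stated rules: AE recording has an end point that the AE-linked analyses do not carry. It should be fixed, but it is a modest problem confined to secondary descriptive analyses.

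The later-cycle AE tables and the kappa bear most of it. The Cycle 1 t-test and the primary endpoints are essentially unaffected, and the Cycle 3 t-test is affected slightly. The tables split by PRO-CTCAE symptom and the summary around progression do not use investigator AEs and are outside the point.

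The kappa drop of about 0.01-0.08 rests on the Japanese median PFS values, progression standing in for switching, uncollected status read as no AE, and the assumed prevalence, sensitivity and specificity. It also depends on the unit of analysis, which SAP 6.2.5 does not state. If sites in fact recorded all AEs to week 24, the problem largely disappears. The documents do not support the inference that the concordance results are invalid, or that the study's main conclusions are biased.

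**What to change.** In SAP 6.2.1, 6.2.2 and 6.2.5:

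- Restrict the investigator-AE tables, their t-tests, the contingency table and the kappa to assessments before the start of a new anticancer therapy. Alternatively, code later non-serious AE status as not collected, and keep recorded SAEs and ongoing AEs in the listings.
- State the unit for the kappa (patient, cycle or week).
- Report the number of assessments excluded per cycle.
- State how this window relates to the one in SAP 6.6.

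In the protocol, clarify that the general statements in Sections 6, 10, 16.1 and 16.2 are read subject to 16.2.4.2. If all AEs were in fact recorded to week 24, say so; no cut is then needed. The SAP 6.1 primary analyses stay as they are.

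Cost: SAP wording and a date filter. Treatment type and duration are already collected in both groups (Protocol 6, note f). The downside is fewer late-cycle observations (in the no-lag illustration, 7-13% fewer patients at Cycle 3 Day 15 and 15-27% fewer at Cycle 6 Day 15). The tables would then describe only patients who have not yet started a new anticancer therapy.
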